5.2.2 Subject Disposition

Reasons for screening failure will be summarized.

The number and percentage of subjects who completed the study will be summarized and the number who discontinued prematurely will be summarized by reason for discontinuation.

5.2.3 Protocol Deviations

Important protocol deviations will be presented as a listing.

5.2.4 Demographic and Other Baseline Characteristics

Demographic and other baseline characteristics for the Safety Analysis Set will be summarized for all subjects using descriptive statistics. Continuous demographic and baseline variables include age, categorical variables include sex, age group and race.

MEDICAL HISTORY

A subject data listing of medical and surgical history will be provided.

5.2.5 Prior and Concomitant Therapy

All investigator terms for medications recorded in the CRF will be coded using the World Health Organization Drug Dictionary (WHO DD) (March 2024). Prior medications will be defined as medications that stopped before the 1st dose of study drug. Concomitant

medications will be defined as medications that (1) started before the 1st dose of study drug and were continuing at the time of the 1st dose of study drug, or (2) started on or after the date of the 1st dose of study drug up to 100 days after the subject's last dose. All medications will be presented in subject data listings.

5.2.6 Treatment Compliance

A listing of study drug administration showing dates, times and volumes of infusion will be presented by subject. Compliance will be determined by reviewing infusion volumes and assessing the number of missed or delayed doses presented in the extent of exposure tables described in Section 5.6.1 below.

5.3 Data Analysis General Considerations

5.3.1 Pooling of Centers

Subjects from all centers will be pooled for all analyses.

5.3.2 Examination of Subgroups

No subgroup analyses are planned for this study.

5.3.3 Handling of Missing Data, Dropouts, and Outliers

See Section 8.1 of this SAP for guidance relating to PK and PD data handling. If no clear reason can be found to explain any anomalous values, then data summaries and graphs, both with and without, the anomalous values will be generated. Appendix 13.1 includes guidance for derivations to address missing responses for cognitive assessments.

5.3.4 Other Considerations

None

5.4 Efficacy Analyses

CC1

5.5 Pharmacokinetic, Pharmacodynamic, Pharmacogenomic, and Other Biomarker Analyses

5.5.1 Pharmacokinetic Analyses

The PK analysis will be performed on the PK Analysis Set. Serum and plasma concentrations of E2814 will be tabulated by nominal sampling time and summarized by dose using summary statistics in Cohort A. Individual serum, plasma and CSF concentration-time profiles will be displayed in linear and semi-log scale presenting actual sampling time on the x-axis.

Serum, plasma and CSF concentrations of E2814 will be listed for each subject by actual sampling time.

The Safety Analysis Set will be used for individual E2814 serum and plasma concentration listings. The PK Analysis Set will be used for the summaries of E2814 serum and plasma concentrations and for summaries and listings of PK parameters.

PK parameters will be derived by noncompartmental analysis using Phoenix WinNonlin software (version 7.0 or newer) according to Eisai's Non-compartmental Pharmacokinetic Analysis Manual (Version 0.1) (NCA-MNL, hereafter).

Serum and plasma E2814 PK parameters will include (but not be limited to) C_{max} , time to reach maximum drug concentration (t_{max}) and area under the concentration-time curve from zero time to the end of the dosing interval ($AUC_{(0-672h)}$) on Days 1 and 85 in Cohort A.

An integrated population analysis of E2814 PK will be performed by pooling data from Cohort A and Cohort B, and from all available studies. For population PK, the details will be described in a separately prepared analysis plan and its report, and the results will be provided in a separate report.

Summary statistics will be tabulated for the PK parameters of E2814 by dose. Summary statistics (n, mean, SD, geometric mean, %CV, median, minimum and maximum) will be presented for all parameters (apart from t_{max} where mean and SD are not required). In addition, geometric mean and %CV will also be presented for all parameters apart from t_{max} .

PK parameters of E2814 for each subject will be listed.

5.5.2 Pharmacodynamic Analyses

The PD Analysis Set will be used for both the listings and summaries of all biomarker CSF and plasma measurements ^{CC1}

Biomarker measurements (fluid and imaging) and change from baseline will be summarized by time point and dose and presented graphically.

These analyses will be done for CSF, plasma and serum. Dose-response relationships will be evaluated.

CCI

Derivations required for BLQ (below the limit of quantification) and ALQ (above the limit of quantification) values are described in Section 8.1.6 below.

Other exploratory biomarker analyses may be performed and reported separately, and the results will not be included in the clinical study report. Details of these analyses would be described in a separate analysis plan.

5.5.3 Pharmacokinetic/Pharmacodynamic Analyses

The relationship between PK and PD will be evaluated by visual inspection using plots. This will include the graphical exploration of the PK/PD relationship between E2814 concentrations and PD biomarker responses in CSF for different E2814 dose exposure levels.

5.5.4 Pharmacogenomic/Pharmacogenetic and Other Biomarker Analyses

PGx analyses may be performed and reported separately. Details of these analyses will be described in a separate analysis plan, and the results will not be included in the clinical study report.

5.6 Safety Analyses

All safety analyses will be performed on the Safety Analysis Set. Safety data, presented by dose, will be summarized using descriptive statistics (eg, n, mean, standard deviation, median, minimum, maximum for continuous variables; n [%] for categorical variables). Safety variables include TEAEs, clinical laboratory parameters, vital signs, and 12-lead

ECG results. Study Day 1 for all safety analyses is defined as the date of the first dose of study drug.

5.6.1 Extent of Exposure

The total number of doses administered at each dose level will be summarized for each subject. This table will also present the number of missed or delayed doses. In addition, a table showing the duration of drug exposure at each dose will be generated for each subject.

5.6.2 Adverse Events

The AE verbatim descriptions (investigator terms from the CRF) will be classified into standardized medical terminology using the Medical Dictionary for Regulatory Activities (MedDRA). Adverse events will be coded to the MedDRA (Version 27) lower level term (LLT) closest to the verbatim term. The linked MedDRA preferred term (PT) and primary system organ class (SOC) will also be captured in the database.

A treatment-emergent adverse event (TEAE) is defined as an AE that emerged during treatment, having been absent at pretreatment (Baseline) or

- Reemerged during treatment, having been present at pretreatment (Baseline) but stopped before treatment, or
- Worsened in severity during treatment relative to the pretreatment state, when the AE is continuous.

During treatment is defined as the period between the administration of study drug and up to 113 days after the last study drug dose. Only those AEs that are treatment emergent will be included in summary tables. All AEs, treatment emergent or otherwise, will be presented in subject data listings.

The TEAEs will be summarized by dose. The incidence of TEAEs will be reported as the number (percentage) of subjects with TEAEs by SOC and PT. A subject will be counted only once within a SOC and PT, even if the subject experienced more than 1 TEAE within a specific SOC and PT. The number (percentage) of subjects with TEAEs will also be summarized by maximum severity (mild, moderate, or severe).

The number (percentage) of subjects with treatment-related TEAEs will be summarized by SOC and PT. Treatment-related TEAEs include those events considered by the investigator to be related to study treatment.

Adverse events will be summarized on the Safety Analysis Set. The number of adverse events, number of subjects with adverse events, and incidence (%) will be calculated by dose and overall. To obtain the incidence (%), the number of subjects with at least 1 event and the percentage of subjects with adverse events by system organ class (SOC) and by preferred term (PT) in the Safety Analysis Set will be calculated.

Separate listings will be provided for subjects with deaths, SAEs, and AEs leading to discontinuation.

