9.1.2.1.1 PHASE 1B TREATMENT PERIOD

[figure not shown]
The Phase 1b Treatment Period will initially allow 8 subjects to receive open-label treatment with 3 IV infusions of 750 mg E2814 every 4 weeks (Q4W) over 12 weeks. Subjects will check into the clinic on the day before dosing but will not be required to stay in the clinic overnight on Day -1 to Day 2, they may instead stay overnight at a nearby hotel and return to the clinic the next day. In addition, subjects will have outpatient visits on Days 15, 29, and 57. On conclusion of the Phase 1b Treatment Period, on Day 84, subjects will check into the clinic and will undergo safety assessments. Subjects will not be required to stay in the clinic overnight on Day 84 to Day 86, they may instead stay overnight at a nearby hotel and return to the clinic the next day. A CSF sample will be collected for assessment of TE and CSF concentrations of E2814 on Day 1 and Day 84. Subjects will then progress to the Phase 2 Treatment Period. Subjects who withdraw from the Phase 1b Treatment Period for reasons other than safety may be replaced.

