5.2 Study Subjects

5.2.1 Definitions of Analysis Sets

The Safety Analysis Set is the group of all allocated subjects who received at least 1 dose of study treatment. At least 1 laboratory, vital sign, or ECG measurement obtained subsequent to at least 1 dose of study treatment is required for inclusion in the analysis of each specific parameter. To assess change from baseline, a baseline measurement is also required. This is the analysis population used for all safety analyses which will be based on as-treated principle.

The Pharmacokinetic Analysis Set is the group of subjects who received at least 1 dose of test drug and had sufficient PK data to derive at least 1 PK parameter.

The Pharmacodynamic Analysis Set is the group of subjects who received at least 1 dose of study drug and had sufficient PD data to derive at least 1 PD parameter.

The definition of these analysis sets is the same for both the Phase 1b (Cohort A) and Phase 2 (Cohort A and Cohort B) Treatment Periods; actual determination of these analysis sets will be made separately for each study period. Data from Cohort A and B will be presented combined. In other words, there will one Safety Analysis Set, one Pharmacokinetic Analysis Set and one Pharmacodynamic Analysis Set.

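### TEAEs are tabulated by dose only as counts and crude percentages, although planned time on dose is very unequal; a common 12-week window and subject-time should be added

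*SAP*

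**What the plan says.** Incidence of TEAEs and SAEs is a primary endpoint (protocol 9.7.1.1.1). SAP 5.6.2 defines the by-dose summary: "The number of adverse events, number of subjects with adverse events, and incidence (%) will be calculated by dose and overall". The percentage of subjects by system organ class and "by preferred term (PT) in the Safety Analysis Set will be calculated". The section gives no person-time rate, no time-to-first-event measure and no fixed window common to the doses. A TEAE counts if it arises "up to 113 days after the last study drug dose".

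Time on dose is set in protocol 9.1.2.1.1, 9.1.2.2, 9.2 and 9.4.1:

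- Cohort A starts with "3 IV infusions of 750 mg E2814 every 4 weeks (Q4W) over 12 weeks". It then has 96 weeks in Phase 2: at least three doses (12 weeks) of 1500 mg, at least three doses (12 weeks) of 3000 mg, and 4500 mg for the rest.
- Cohort B receives 3000 mg for up to 52 weeks.

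SAP 5.6.1 tabulates doses and duration at each dose level per subject, but nothing links that table to the adverse event summary.

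On analysis sets, SAP 5.2.1 first says that the definition is "the same for both the Phase 1b (Cohort A) and Phase 2 (Cohort A and Cohort B) Treatment Periods" and that "actual determination of these analysis sets will be made separately for each study period". It then says "Data from Cohort A and B will be presented combined" and "In other words, there will one Safety Analysis Set". It also calls the safety analyses as-treated.

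**The concern.** The more weeks a subject spends at a dose, the more likely at least one event is recorded there. A crude percentage by dose therefore mixes the effect of the dose with the length of stay on it. Here the length of stay is tied to dose by the titration schedule, and at 3000 mg it also differs between the two cohorts pooled in that column.

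At stake is how the by-dose tables for a primary endpoint are read. A reader who looks across the four columns can see a rise, or a rise and fall, that reflects exposure alone.

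Two smaller gaps make the columns harder to read. SAP 5.6.2 does not name the number of subjects under each dose column. It also gives no rule for assigning an event to a dose, although the same Cohort A subjects may pass through four doses.

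**Working it through.** The documents give no adverse event rate and no expected incidence, so there is no planned figure to reproduce. The check starts from the schedule.

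**Inputs**

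- Up to 8 subjects in Cohort A and up to 5 in Cohort B (protocol 9.3, SAP 4).
- Planned time on dose as set out above.
- Assumptions: one constant hazard at every dose, with p = 25% (or 10%) of subjects having a first event per 12 weeks; each dose column counted afresh; time on dose only; full enrolment; no dropout.

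**1. Limits on time.** The maximum at 4500 mg is 96 − 12 − 12 = 72 weeks. That cap belongs to 4500 mg alone. Protocol 9.2 sets no ceiling at 3000 mg, so a Cohort A subject who starts 4500 mg late could spend 96 − 12 − 4 = 80 weeks at 3000 mg. The CSF sample on Day 169 (protocol 9.5.1.3.1) fits 12 weeks at 1500 mg: (169 − 85)/7 = 12. The readable text gives no day for the first 4500 mg dose, so two paths are used for 1500/3000/4500 mg:

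- fastest: 12 + 12 + 72 = 96 weeks
- slower, assumed: 12 + 48 + 36 = 96 weeks

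**2. Subject-weeks**

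| Path | 750 mg | 1500 mg | 3000 mg | 4500 mg |
|---|---|---|---|---|
| Fastest | 8×12 = 96 | 96 | 96 + 5×52 = 356 | 8×72 = 576 |
| Slower | 96 | 96 | 8×48 + 260 = 644 | 8×36 = 288 |

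**3. Crude incidence** over w weeks is 1 − (1 − p)^(w/12). With p = 0.25 this gives 25.0% at 12 weeks, 57.8% at 36, 68.4% at 48, 71.3% at 52 and 82.2% at 72. The pooled 3000 mg column is (8×0.250 + 5×0.713)/13 = 42.8% on the fastest path and (8×0.684 + 5×0.713)/13 = 69.5% on the slower one.

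| Path, p | 750 mg | 1500 mg | 3000 mg | 4500 mg |
|---|---|---|---|---|
| Fastest, 25% | 25% | 25% | 43% | 82% |
| Slower, 25% | 25% | 25% | 70% | 58% |
| Fastest, 10% | 10% | 10% | 20% | 47% |
| Slower, 10% | 10% | 10% | 35% | 27% |

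The true hazard is identical in every cell of a row. On the fastest path with p = 25%, the 43% at 3000 mg hides 25% in Cohort A and 71% in Cohort B.

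**4. What the added measures would show.** With p = 25%, the percentage in the first 12 weeks on dose is 25% in every column. The rate of first events is −ln(0.75)/12 × 52 = 1.25 per subject-year in every column. Both are flat, as they should be with no dose effect.

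**5. Precision.** Take 2 of 8 subjects with an event over 12 weeks, with events assumed midway. Subject-time is (6×12 + 2×6)/52 = 1.62 years and the rate is 2/1.62 = 1.24 per subject-year. The exact Poisson 95% interval is 0.15 to 4.47.

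**6. The window.** The SAP window is 113 days. Adverse events are recorded through the last visit, and follow-up lasts 12 weeks, or 84 days (protocol 9.5.1.4.1, 9.1.2.3); 113 − 84 = 29 days. SAEs are collected for 100 days (protocol 9.5.4.1); 113 − 100 = 13 days. Protocol 9.5.1.4.1 also has adverse events followed for 16 weeks, or 112 days, which matches the SAP window to within a day.

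**The case against.** The strongest reply is that no between-dose safety comparison is planned. Dose-response is to be evaluated only for pharmacodynamics (protocol 9.7.1.7.2, SAP 5.5.2), and the sample is meant for initial safety. Protocol 9.7.1.8.2 itself plans by-dose subject counts and percentages, so the SAP follows the protocol here. With at most 13 subjects, SAP 5.6.1 shows each subject's exposure and every event is listed, so a reader can derive a crude rate. Rates would be very imprecise, they assume a roughly constant hazard, which may not suit infusion reactions, and dose stays confounded with time in a forced titration.

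All of this stands, and it limits the size of the point. It does not make the crude columns comparable. The 12-week percentage also needs no constant-hazard assumption.

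Three stronger readings are tempting, and the documents do not support them:

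- *Every dose column is divided by all 13 subjects.* A reader might infer this from the reference to the Safety Analysis Set and the single combined set. The as-treated wording and the by-dose presentation point instead to the subjects who received each dose, which is the count planned in protocol 9.7.1.3. The specifications and table shells (SAP 9 and 11) are separate documents and may already fix it.
- *The 113-day window is an error that dilutes the rates.* The SAP calculates no rate, and the window is close to the 16-week follow-up. The passages need reconciling, no more.
- *The plan will reverse a true dose trend.* The two patterns above come from two assumed titration paths with no dose effect, so no true trend is reversed.

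**Conclusion.** The point holds as a limitation of the planned summary. By-dose TEAE percentages without any allowance for exposure can differ widely between columns when the risk is the same. The illustration gives 25% at 750 mg against 82% at 4500 mg on the fastest titration with a hazard of 25% per 12 weeks, or 10% against 47% with 10% per 12 weeks. These figures rest on the assumed hazard, full enrolment, no dropout and the assumed titration path; the actual size depends on when subjects moved to 4500 mg.

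No error rate or formal conclusion is affected. The gain is in reading the tables, so the priority is low. The denominator, the event-to-dose rule and the wording of SAP 5.2.1 are clarifications that the shells or specifications may already settle.

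**What to change.** Keep the planned counts and percentages in SAP 5.6.2 and add:

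1. the percentage of subjects with a TEAE in the first 12 weeks on each dose, with the number observed for the full 12 weeks;
2. subject-time at risk, and subjects with an event per subject-time, for each dose;
3. the 3000 mg column split by cohort.

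As clarifications:

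- State that each dose column's denominator is the subjects with at least one infusion at that dose.
- State the rule that assigns an event to a dose, or cite the shells or specifications that hold these rules.
- Reconcile the two sentences on analysis sets in SAP 5.2.1.
- Reconcile the 113-day window with recording through the last visit, the 12-week follow-up, the 16-week adverse event follow-up and the 100-day SAE collection. Count as time at risk only the period in which events were actually recorded.

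The cost is a short SAP edit and a few table columns, using exposure data already tabulated under SAP 5.6.1. The rates should carry their confidence intervals and a note that they assume a roughly constant hazard. The note should also say that neither added measure separates dose from time since first treatment.

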5.6.3 Laboratory Values

Laboratory results will be summarized using Système International (SI) units, as appropriate. For all quantitative parameters listed in protocol Section 9.5.1.4.4 Safety Assessments (Laboratory Measurements), the actual value and the change from baseline to each postbaseline visit and to the end of treatment will be summarized by visit using descriptive statistics. Qualitative parameters listed in protocol Section 9.5.1.4.4 will be summarized using frequencies (number and percentage of subjects), and changes from baseline to each postbaseline visit and to end of treatment will be reported using shift tables. Percentages will be based on the number of subjects with both nonmissing baseline and relevant postbaseline results.

Laboratory test results will be graded or assigned a low/normal/high (LNH) classification according to whether the value was below (L), within (N), or above (H) the laboratory parameter's reference range. Each laboratory parameter will be assessed based on shift tables that compare the baseline LNH classification to the LNH classification at each postbaseline visit and at the end of treatment.

Appendix 13.2 presents the criteria (based upon Common Terminology Criteria for Adverse events (CTCAE) Version 5.0) that will be used to identify subjects with treatment-emergent markedly abnormal laboratory values (TEMAVs). Except for phosphate, a TEMA V is defined as a postbaseline value with an increase from baseline to a grade of 2 or higher. For phosphate, a TEMA V is defined as a postbaseline value with an increase from baseline to a grade of 3 or higher. A listing of subjects with markedly abnormal laboratory values will be generated, which will be ordered by subject.

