9.5.1.4.4 LABORATORY MEASUREMENTS

Clinical laboratory tests to be performed, including hematology, clinical chemistry, and urinalysis, are summarized in Table 3. Subjects should be in a seated or supine position during blood collection. The Schedule of Procedures/Assessments ([Table 4](#) or [Table 5](#)) shows the visits and time points at which blood for clinical laboratory tests and urine for urinalysis will be collected in the study. (revised per Amendment 03)

Table 3 Clinical Laboratory Tests

Category	Parameters
Hematology	Hematocrit, hemoglobin, platelets, RBC count, and WBC count with differential (basophils, eosinophils, lymphocytes, monocytes, neutrophils), fibrinogen, prothrombin time, aPTT, INR
Clinical chemistry	
Electrolytes	Calcium, chloride, potassium, sodium
Liver function tests	Alanine aminotransferase, alkaline phosphatase, aspartate aminotransferase, gamma glutamyl transpeptidase, direct bilirubin, total bilirubin
Renal function tests	Blood urea/blood urea nitrogen, creatinine
Blood chemistry	Free T3, free T4, TSH, Vitamin B12, methylmalonic acid, C-reactive protein
Other	Albumin, total cholesterol, globulin, glucose, lactate dehydrogenase, inorganic phosphorus, total protein, protein fraction, triglycerides, uric acid, HbA _{1c} , hepatitis viral screen (HBcAb, HBsAg, HCVAb), HIV
Urinalysis	Glucose, ketones, occult blood, pH, protein, sediment (RBCs, WBCs, bacteria, casts, crystals, epithelial cells), specific gravity

HbA_{1c} levels and viral screen will be done at Screening only.

Total fibrinogen levels (measured in plasma using immunological methods) and functional fibrinogen (measured in plasma using the Clauss method) will be determined.

aPTT = activated partial thromboplastin time, HbA_{1c} = glycosylated hemoglobin, HBcAb = hepatitis B core antibody, HBcAg = hepatitis B core antigen, HBsAg = hepatitis B surface antigen, HCVAb = hepatitis C virus antibody, HIV = human immunodeficiency virus, INR = international normalized ratio, RBC = red blood cell, WBC = white blood cell.

Clinical laboratory tests will be performed by a central laboratory. All blood and urine samples will be collected and sent to the central laboratory on the day of collection unless

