9.7.1.8.3 LABORATORY VALUES

Laboratory results will be summarized using Système International units, as appropriate. For all quantitative parameters listed in [Section 9.5.1.4.4](#), the actual value and the change from baseline to each postbaseline visit and to the end of treatment (defined as the last on-treatment value) will be summarized by visit and dose using descriptive statistics. Qualitative parameters listed in [Section 9.5.1.4.4](#) will be summarized using frequencies (number and percentage of subjects), and changes from baseline to each postbaseline visit and to end of treatment will be reported using shift tables. Percentages will be based on the number of subjects with both nonmissing baseline and relevant postbaseline results.

Laboratory test results will be assigned a low/normal/high (LNH) classification according to whether the value was below (L), within (N), or above (H) the laboratory parameter's reference range. Within-treatment comparisons for each laboratory parameter will be based on 3-by-3 tables (shift tables) that compare the baseline LNH classification to the LNH classification at each postbaseline visit and at the end of treatment. Similar shift tables will also compare the baseline LNH classification to the LNH classification for the highest and lowest value during the Treatment Period.

[Appendix 1](#) (Sponsor's Grading for Laboratory Values) presents the criteria that will be used to identify subjects with treatment-emergent markedly abnormal laboratory values (TEMAVs). Except for phosphate, a TEMA is defined as a postbaseline value with an increase from baseline to a grade of 2 or higher. For phosphate, a TEMA was defined as a postbaseline value with an increase from baseline to a grade of 3 or higher. A listing of subjects with markedly abnormal laboratory values will be generated, which will be ordered by dose and subject.

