7 CHANGES IN THE PLANNED ANALYSES

There were no changes to the planned analyses.

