13.2 Sponsor's Grading for Determining Markedly Abnormal Laboratory Results

The following table of Sponsor's Grading for Laboratory Values is copied from the protocol, Appendix 1.

Sponsor's Grading for Laboratory Values

	Grade 1	Grade 2	Grade 3	Grade 4
BLOOD/BONE MARROW				
Hemoglobin	<LLN – 10.0 g/dL <LLN – 100 g/L <LLN – 6.2 mmol/L	<10.0 – 8.0 g/dL <100 – 80 g/L <6.2 – 4.9 mmol/L	<8.0 g/dL <80 g/L <4.9 mmol/L; transfusion indicated	life-threatening consequences; urgent intervention indicated
Leukocytes (total WBC)	<LLN – 3.0×10 ⁹ /L <LLN – 3000/mm ³	<3.0 – 2.0×10 ⁹ /L <3000 – 2000/mm ³	<2.0 – 1.0×10 ⁹ /L <2000 – 1000/mm ³	<1.0×10 ⁹ /L <1000/mm ³
Lymphocytes	<LLN – 800/mm ³ <LLN – 0.8×10 ⁹ /L	<800 – 500/mm ³ <0.8 – 0.5×10 ⁹ /L	<500 – 200/mm ³ <0.5 – 0.2×10 ⁹ /L	<200/mm ³ <0.2×10 ⁹ /L
Neutrophils	<LLN – 1.5×10 ⁹ /L <LLN – 1500/mm ³	<1.5 – 1.0×10 ⁹ /L <1500 – 1000/mm ³	<1.0 – 0.5×10 ⁹ /L <1000 – 500/mm ³	<0.5×10 ⁹ /L <500/mm ³
Platelets	<LLN – 75.0×10 ⁹ /L <LLN – 75,000/mm ³	<75.0 – 50.0×10 ⁹ /L <75,000 – 50,000/mm ³	<50.0 – 25.0×10 ⁹ /L <50,000 – 25,000/mm ³	<25.0×10 ⁹ /L <25,000/mm ³
METABOLIC/LABORATORY				
Albumin, serum- low (hypoalbuminemia)	<LLN – 3 g/dL <LLN – 30 g/L	<3 – 2 g/dL <30 – 20 g/L	<2 g/dL <20 g/L	life-threatening consequences; urgent intervention indicated
Alkaline phosphatase	>ULN – 2.5×ULN if baseline was normal; 2.0 – 2.5×baseline if baseline was abnormal	>2.5 – 5.0×ULN if baseline was normal; >2.5 – 5.0×baseline if baseline was abnormal	>5.0 – 20.0×ULN if baseline was normal; >5.0 – 20.0×baseline if baseline was abnormal	>20.0×ULN if baseline was normal; >20.0×baseline if baseline was abnormal
ALT	>ULN – 3.0×ULN if baseline was normal; 1.5 – 3.0×baseline if baseline was abnormal	>3.0 – 5.0×ULN if baseline was normal; 3.0 – 5.0×baseline if baseline was abnormal	>5.0 – 20.0×ULN if baseline was normal; >5.0 – 20.0×baseline if baseline was abnormal	>20.0×ULN if baseline was normal; >20.0×baseline if baseline was abnormal
AST	>ULN – 3.0×ULN if baseline was normal; 1.5 – 3.0×baseline if baseline was abnormal	>3.0 – 5.0×ULN if baseline was normal; 3.0 – 5.0×baseline if baseline was abnormal	>5.0 – 20.0×ULN if baseline was normal; >5.0 – 20.0×baseline if baseline was abnormal	>20.0×ULN if baseline was normal; >20.0×baseline if baseline was abnormal

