Bilirubin (hyperbilirubinemia)	>ULN – 1.5×ULN if baseline was normal; 1.0 – 1.5×baseline if baseline was abnormal	>1.5 – 3.0×ULN if baseline was normal; 1.5 – 3.0×baseline if baseline was abnormal	>3.0 – 10.0×ULN if baseline was normal; 3.0 – 10.0×baseline if baseline was abnormal	>10.0×ULN if baseline was normal; >10.0×baseline if baseline was abnormal
Calcium, serum-low (hypocalcemia)	<LLN – 8.0 mg/dL <LLN – 2.0 mmol/L Ionized calcium <LLN - 1.0 mmol/L	<8.0 – 7.0 mg/dL <2.0 – 1.75 mmol/L Ionized calcium <1.0 - 0.9 mmol/L; symptomatic	<7.0 – 6.0 mg/dL <1.75 – 1.5 mmol/L Ionized calcium <0.9 - 0.8 mmol/L; hospitalization indicated	<6.0 mg/dL <1.5 mmol/L Ionized calcium <0.8 mmol/L; life-threatening consequences
Calcium, serum-high (hypercalcemia)	>ULN – 11.5 mg/dL >ULN – 2.9 mmol/L Ionized calcium >ULN - 1.5 mmol/L	>11.5 – 12.5 mg/dL >2.9 – 3.1 mmol/L Ionized calcium >1.5 - 1.6 mmol/L; symptomatic	>12.5 – 13.5 mg/dL >3.1 – 3.4 mmol/L Ionized calcium >1.6 - 1.8 mmol/L; hospitalization indicated	>13.5 mg/dL >3.4 mmol/L Ionized calcium >1.8 mmol/L; life- threatening consequences

Sponsor's Grading for Laboratory Values

	Grade 1	Grade 2	Grade 3	Grade 4
Cholesterol, serum-high (hypercholesterolemia)	>ULN – 300 mg/dL >ULN – 7.75 mmol/L	>300 – 400 mg/dL >7.75 – 10.34 mmol/L	>400 – 500 mg/dL >10.34 – 12.92 mmol/L	>500 mg/dL >12.92 mmol/L
Creatinine	>ULN – 1.5×ULN	>1.5 - 3.0×baseline; >1.5 – 3.0×ULN	>3.0×baseline; >3.0 – 6.0×ULN	>6.0×ULN
Fibrinogen plasma-low	>125 - 175 mg/dL	>80 – 125 mg/dL	50- 80 mg/dL	<50 mg/dL
Fibrinogen plasma-high	425 - 500 mg/dL	>500 - 600 mg/dL	>600 - 700 mg/dL	> 700 mg/dL
GGT (γ -glutamyl transpeptidase)	>ULN – 2.5×ULN if baseline was normal; 2.0 - 2.5 x baseline if baseline was abnormal	>2.5 – 5.0×ULN if baseline was normal; >2.5 - 5.0 x baseline if baseline was abnormal	>5.0 – 20.0×ULN if baseline was normal; >5.0 - 20.0 x baseline if baseline was abnormal	>20.0×ULN if baseline was normal; >20.0 x baseline if baseline was abnormal
Glucose, serum-high (hyperglycemia)	Abnormal glucose above baseline with no medical intervention	Change in daily management from baseline for a diabetic; oral antihyperglycemic agent initiated; workup for diabetes	Insulin therapy initiated; hospitalization indicated	life-threatening consequences; urgent intervention indicated

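### SAP 5.6.3 omits the protocol's highest- and lowest-value laboratory shift tables and Appendix 13.2 adds fibrinogen grades, while SAP Section 7 declares no changes

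*SAP*

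**What the plan says.** Protocol 9.7.1.1.1 places laboratory parameters in the first primary endpoint. Protocol 9.7.1.8.3 specifies two kinds of LNH shift table: one for each postbaseline visit and the end of treatment, and a second that must "compare the baseline LNH classification to the LNH classification for the highest and lowest value during the Treatment Period".

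SAP 5.6.3 keeps the first kind. Values and changes to each visit and "to the end of treatment will be summarized by visit using descriptive statistics", and each parameter is assessed with "shift tables that compare the baseline LNH classification to the LNH classification at each postbaseline visit and at the end of treatment". The second kind does not appear there or elsewhere in the SAP text.

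Both documents define a treatment-emergent markedly abnormal laboratory value (TEMAV) as a rise from baseline to Grade 2 or higher, or Grade 3 or higher for phosphate. For these the SAP provides: "A listing of subjects with markedly abnormal laboratory values will be generated, which will be ordered by subject". The grades come from SAP Appendix 13.2, which says that the Sponsor's "Grading for Laboratory Values is copied from the protocol, Appendix 1". That table contains a row headed "Fibrinogen plasma-low" and a matching row for high fibrinogen.

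SAP Section 3 names protocol Amendment 04 as the version it implements. Section 7 states: "There were no changes to the planned analyses".

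**The concern.** A highest/lowest shift table answers a basic safety question: of the subjects who started in range, how many went out of range at any time on treatment? Visit tables answer a different one: how many were out of range at a given visit. With at most 8 subjects in Cohort A and 5 in Cohort B, abnormalities are likely to be few and spread over visits, so the two answers can differ widely.

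The fibrinogen rows bring a further parameter under the TEMAV rule. Protocol Table 3 provides for both total and functional fibrinogen, and the new rows do not say which is graded. A reader who relies on the statement that the table was copied, or on Section 7, would not look for either change.

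**Working it through.** The plan gives no figure to reproduce. The check is a comparison of texts, followed by two small counts.

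**1. Protocol against SAP**

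| Item | Protocol | SAP |
|---|---|---|
| LNH shifts by visit and end of treatment | Required (9.7.1.8.3) | Kept (5.6.3) |
| LNH shifts to highest and lowest value on treatment | Required (9.7.1.8.3) | Absent |
| Order of TEMAV listing | Dose, then subject | Subject |
| Rows in grading table | 24 (Appendix 1) | 26 (13.2) |
| Fibrinogen rows | 0 | 2 (low, high) |
| Declared changes | – | None (Section 7) |

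Row count: Appendix 1 has 5 blood/bone marrow rows and 19 metabolic rows, 5 + 19 = 24. SAP 13.2 has the same rows plus two for fibrinogen, 24 + 2 = 26.

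**2. What per-visit tables can say about subjects ever out of range**

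Let c(v) be the number of subjects high at visit v, n the number of subjects, and E the number ever high. Then

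max c(v) ≤ E ≤ min(n, Σ c(v)).

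Illustration, not taken from the documents except for n = 5, the Cohort B maximum: five visit tables with one high value each.

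- Lower bound: 1, and 1/5 = 20%.
- Upper bound: min(5, 1+1+1+1+1) = 5, and 5/5 = 100%.

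The visit tables are identical at both ends of this range. A highest-value table would give E directly.

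**3. Whether the TEMAV listing can stand in**

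It has two limits.

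*Threshold.* With a normal baseline, an ALT up to 3.0×ULN is Grade 1 in SAP 13.2. It is therefore out of range but not a TEMAV. A highest-value shift table would show it as normal to high.

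*Coverage.* The count uses the quantitative blood tests in protocol Table 3. HbA1c and the viral tests are left out because the table note says their "levels and viral screen will be done at Screening only". Urinalysis is left out, and fibrinogen is counted once.

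| Group | Tests | With a row in SAP 13.2 |
|---|---|---|
| Hematology | 14 | 6 |
| Electrolytes | 4 | 3 |
| Liver | 6 | 5 |
| Renal | 2 | 1 |
| Blood chemistry | 6 | 0 |
| Other | 10 | 6 |
| Total | 42 | 21 |

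Without a row: 42 − 21 = 21 (50%). These include PT, aPTT, INR, eosinophils, direct bilirubin, blood urea nitrogen and LDH. If the six blood chemistry tests are also Screening only (the schedule is redacted), the count is 21 − 6 = 15 of 42 − 6 = 36 (42%).

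This count shows how far the listing falls short as a substitute. It does not measure the departure: under protocol Appendix 1, without fibrinogen rows, 22 of 42 tests are ungraded. The difference is that the protocol provided highest/lowest tables for those tests and the SAP does not.

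**The case against.** The strongest reply is that little is lost. The trial is descriptive and has at most 13 subjects. Every quantitative test still gets descriptive statistics by visit, including minimum and maximum, and LNH shifts by visit. The TEMAV rule applies to any postbaseline value. SAP Section 11 leaves the content of all tables and listings to separate shells, and a full laboratory listing there would show every out-of-range subject. The fibrinogen rows add detection for a test the protocol already measures.

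Part of this stands. Marked abnormalities in graded tests remain identifiable by subject, and the fibrinogen fault is one of accuracy and disclosure, since the added grading may well be useful. The new order of the TEMAV listing is only sorting. The rest does not close the gap. A minimum or maximum at a visit shows that someone reached that value, but not how many subjects did so over the treatment period. The SAP text names listings for markedly abnormal laboratory values and for vital signs, but none for all laboratory values. The shells are not among the documents, so they cannot be credited.

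A reader might infer something stronger: that dose has been removed from the laboratory, vital-sign and ECG summaries, because SAP 5.6.3 to 5.6.5 say only by visit where protocol 9.7.1.8.3 to 9.7.1.8.5 say dose and visit. The documents do not support that. The parent section, SAP 5.6, says safety data are presented by dose and names all three data types. SAP 5.2.1 does say that the cohorts are presented combined, but it goes on to explain this as having one analysis set of each kind, which does not override 5.6. It is a wording mismatch and shows no clear departure for vital signs or ECGs.

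Nor does the point rest on unscheduled results. Protocol 9.5.4.3.2 foresees them, but it concerns liver tests that all have grades.

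**Conclusion.** The point holds for laboratory data. The SAP text omits one required family of tables, and with it the number of subjects ever out of range on treatment. It also adds two fibrinogen rows to a table described as copied, which extends the TEMAV rule. Section 7 is wrong to say there were no changes. These conclusions rest on the texts alone and need no assumption about the redacted visit schedule.

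The effect is confined to descriptive safety reporting, but on part of a primary endpoint. No test, alpha level or sample size changes. The 20% to 100% range is an illustration, and the 21 of 42 count depends on the counting rules stated above. The one open matter is whether the unseen table shells already include the missing tables; if they do, the SAP text still needs correcting.

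**What to change.** - In SAP 5.6.3, restore the LNH shift tables from baseline to the highest and to the lowest value during the Treatment Period.
- In SAP 13.2, correct the statement that the table is copied from Appendix 1, and say whether the fibrinogen rows apply to total fibrinogen, functional fibrinogen or both.
- In SAP Section 7, record the fibrinogen rows and any other departure that is kept, such as the order of the TEMAV listing, each with a reason.
- As a minor alignment, write by dose and visit in SAP 5.6.3, 5.6.4 and 5.6.5, to match SAP 5.6 and the protocol.

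The cost is SAP wording and table shells. The restored tables use laboratory data already being collected, so no new assessment is needed.
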